7.3 Data Collection

Objective 2 will include two forms of data collection: 1) participant questionnaires at enrollment (baseline), midpoint (2-4 months), and endpoint (at least 6 months post enrollment) follow-up; 2) clinical and appointment data from the EHR. The baseline questionnaire will be administered to all participants at the time of consenting to participate in the study in order to collect basic sociodemographic characteristics, such as gender identity, education, marital status, income, residence, and other characteristics shown to influence ART outcomes (Mills et al., 2006). The questionnaire will also collect data on potential predictors of intervention success, including unmet needs, satisfaction with care and stigma. (Appendix F). At the midpoint (2-4 months post enrollment) and endpoint (at least 6 months post enrollment), the data will be collected again, using the same data collection instrument. The midpoint data collection and endpoint data collection target dates will be determined by study staff and participants at the first enrollment appointment. For Cohort 1 and Cohort 2 participants, these dates will coincide with their scheduled injections if possible, for convenience.

One week before each target data collection date, study staff will contact the participant using the preferred communication method they specified on their Locator Form at enrollment. Once a data collection date has been determined, study staff will contact participant through their preferred means of communication one day prior to appointment for a reminder.

At the time of data collection, the participant and study staff will meet at determined study location (either Project Trust or CID). Study staff will bring the Participant Folder, Log Book and a ClinCard. The participant will complete the participant survey. If the participant is in Cohort 1 or 2 and is scheduled to receive their

Protocol Title: **CAB-RPV LA Implementation Strategies for High-Risk Populations**

injection at this appointment, the survey can be completed during the 15-minute observation period after the injection.

The clinical and appointment data to be collected from the EHR on all study participants will include clinical endpoints (appointment adherence, viral load, CD4, etc.). Data on clinical endpoints will be collected from their EHR at enrollment at each data collection period using the Chart Review Tool (Appendix E).

All study participants will be provided a ClinCard worth \$25 once they have completed the baseline survey. ClinCards will be kept in the same locked filing cabinet as participant folders and the Log Book. Study staff are all trained in how to register and activate the ClinCard. ClinCards will continue to be provided at the completion of the three-month and six-month follow-up surveys. Each time a participant receives a ClinCard, it will be recorded in the Log Book. Completed Surveys will be kept in the Participant Folder, to be placed in the locked filing cabinet of the Project Manager.

7.4 Clinician Training

All clinicians who are to administer CAP-RPV LA in any setting related to this study will complete full Good Clinical Practice training, and have read the Cabenuva instructions for use, all information regarding contraindications, warnings and precautions, drug interactions, and possible adverse effects. The package insert will be attached to the BUMC IRB submission. All clinicians administering injections will review the ViiV Healthcare Cabenuva training video and participate in injection training.

All clinicians will be trained by ViiV in administering intramuscular gluteal injections. All study staff will be trained in the cold chain storage procedure, including transportation requirements and thawing instructions by BMC Pharmacy Staff. All clinical study staff have basic life support training and are CPR certified. All clinical study staff will be trained during a staff meeting on adverse event reporting per both BMC and ViiV. Adverse Event Reporting forms will be those specified by ViiV and will be attached to the IRB submission.

All clinical staff are familiar with non-traditional care setting sites, and when off site will follow the protocols set forth by staff at those sites. All study staff are aware of and trained in how to follow adverse event protocol (see Sections on Adverse Events, Serious Adverse Events and Post Injection Reactions" for specific protocol details). This training will occur at a clinical study staff meeting at Project Trust, which is located adjacent to the BMC campus. In the case of serious adverse events, participants will be brought to the BMC Emergency Department.

7.5 Medication Acquisition and Storage

For the optional oral lead-in, the study clinician will write the prescription for the participant and send it to the BMC pharmacy. Depending on the participants preference, either PT staff or the participant themselves will go pick the prescription up from the pharmacy and the participant will begin taking the oral lead-in medication on that day. The participant will keep their medication for the duration of their lead in.

In order to keep CAB-RPV LA at the determined temperature necessary, (2°C to 8°C; 36°F to 46°F), the medication will be kept in a cooler bag from the time that it is picked up from the BMC pharmacy until it is brought over to PT to be stored until use. The refrigerator at PT is in the Nurse Practitioner's office; the refrigerator itself has a locked door, and the office door is also locked when not in use. The refrigerator is temperature monitored in conjunction with BMC requirements. A study clinician will write the CAB-RPV LA prescription and submit through Epic, the EHR system employed by BMC. The study clinician will go through the prior authorization procedure in collaboration with the specialty pharmacy. The specialty pharmacy team and study staff will have a standing weekly check-in to determine how many injections are scheduled for

Protocol Title: **CAB-RPV LA Implementation Strategies for High-Risk Populations**

each week. The study staff will then go pick up all the prescriptions for the week at the pharmacy, and transport them to PT in the cooler bag. Staff will wait until participant has arrived at Project Trust to remove the injection from the refrigerator to begin the thawing process. If the participant does not show up for their scheduled injection, the medication will be left in the refrigerator until the participant is ready for administration.

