7.6 Injection Process and Safety Procedures

For patients enrolled in Cohort 1, injection procedures will be as follows:

- 15 minutes prior to the scheduled appointment time, the study clinician will remove the injection from refrigeration.
- Injections will be administered by a licensed healthcare professional (physician, nurse, nurse practitioner).
 - a. A complete dose will include two injections: one injection of cabotegravir and one injection of rilpivirine.
 - b. Each injection will be administered at separate gluteal injection sites during the same visit, with the ventrogluteal site recommended.
 - c. The clinician will consider the body mass index (BMI) of the patient to ensure that the needle length is sufficient to reach the gluteus muscle. Longer needle lengths (not included in the dosing kit) may be required for patients with higher BMI (greater than 30 kg/m²) to ensure that injections are administered intramuscularly as opposed to subcutaneously.
- The clinician and the participant will determine the target date for the next injection, which will occur between 25-32 days from initial injection. This discussion will happen while the participant waits for 15 minutes to ensure that no immediate adverse effects occur. This encounter and next planned injection date will be documented in the study Log Book by study staff. During this 15-minute period, the participant may also complete follow-up questionnaires if they are due for their three-month or six-month follow-up survey.
- Once the participant receives their second injection, they may discuss with their clinician whether they want to continue to receive their injection monthly, or whether they want to move to a bi-monthly schedule. The same procedures (confirming appointments in advance, removal from refrigerator, injection administration, monitoring period post-injection, scheduling of next injection, documentation in study log) will be used for follow-up injections
- Once the participant has been enrolled for at least 6 months in the study, they will be given the option to remain on CAB-RPV LA
 - a. That administration can take place either at PT or at CID depending on the participants preferences
 - b. If the participant wishes to receive their injection at CID, the study clinician will reach out to the participants CID provider so that the participant can begin to schedule their injections at CID

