7.8 Dosing Errors & Other Errors

All efforts will be made to ensure there are no dosing errors. However, the following procedures are in place to address dosing errors or other errors:

- **Dosing Error – Too Large of a Dose Administered:** The study staff will contact the participant immediately following recognition of error and inform them about their error. If dose was the equivalent or higher of the loading dose (600 mg/900 mg 3 ml), then study staff would change next target injection date to be 2 months after dose given in error, and then resume maintenance doses moving forward.
- **Dosing Error – Too Small of a Dose Administered:** Study staff will contact the participant immediately following the recognition of the dosing error.
- **Incorrect storage of Cabenuva:** If it is determined that the injection has been incorrectly stored, the affected doses will be disposed of in a hazardous waste container.
- **Healthcare Provider Needlestick Injuries:**
 - Wash/rinse wound or exposed area immediately.
 - Report incident to Study Staff Supervisor

Protocol Title: **CAB-RPV LA Implementation Strategies for High-Risk Populations**

- Exposed individual should call the BMC Working Well Clinic at [contact] or visit the clinic on the 7th floor of the Doctor's Office Building.
- Print and Complete all forms listed below that are found on the BMC Employee Hub:
 - Blood and Bodily Fluids Exposure Incident Form and scan and email to [contact]
 - Source Patient Requisition Form
 - Source Patient Testing Release Form – other staff member must consent patient, have both printed name and signature at the bottom of the page of source patient and ordering provider who consented patient
 - Test results are reported to the Working Well Clinic who will notify individual of results

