9.0 Safety Review

This study is not intended to assess the efficacy of CAB-RPV LA as a medication; rather it is an implementation study to examine changing the service site of care delivery. CAB RPV-LA is already an approved medication that can be delivered to PLWH who receive care at CID. Thus, a DSMB is not required. However, in order to monitor safety of study participants in the pilot implementation trial, we will do the following: Any issues with the injections themselves will be recorded in logbooks. Special attention will be given to any medical issues related to the injections, including perceived soreness, fatigue, and other unintended consequences throughout the trial and standard referral to BMC will be made in such cases. We will also report all medication errors identified to the sponsor as required by ViiV. During analysis, we will categorize the errors into the four groups identified by ViiV in order to capture severity: medication errors associated with adverse events, medication errors without harm, intercepted (near miss) medication errors, and potential medication errors. VH has requested that all implementation studies involving the use of medications collect and report the following potential medical errors associated with administration of a medication: 1) Dosing errors, including incorrect loading dose, multiple loading doses, errors in maintenance dose (e.g. 3ml given instead of 2ml by accident), excess dose (e.g. two injections of one medication instead of one injection of each); 2) Faulty technique, including accidental IV or SC leading to partial IV administration, needle breakage, use of wrong needle, failure to fill syringe with medicine appropriately, multiple injections /re-injection on the same site (minimum gap), leakage from vial or syringe, leakage from injection site, healthcare provider needlestick injuries; 3) Other medication errors including delivery at a site other than the gluteal region, one injection of each drug but not on the same visit, storage at the wrong temperature, time outside refrigeration, use of expired medicine. These events will be reported through the Non-Serious Adverse Events/Adverse Drug Reaction Pages, Associated Person Safety Reporting Information and Authorization Letter, Medical Device or Combination Product with Device Deficiency/Incident Report Form, all attached in the Appendix of this document

Protocol Title: **CAB-RPV LA Implementation Strategies for High-Risk Populations**

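### Sections 7.5 and 7.6 give conflicting triggers for taking a Cohort 1 injection out of the refrigerator, and neither says how a dose already removed for a no-show is handled or recorded

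*Combined protocol and SAP*

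**What the plan says.** Section 7.5 covers acquisition and storage. It gives a required temperature range ("In order to keep CAB-RPV LA at the determined temperature necessary, (2°C to 8°C; 36°F to 46°F") and makes arrival the event that starts thawing: "Staff will wait until participant has arrived at Project Trust to remove the injection from the refrigerator to begin the thawing process". It then covers non-attendance: "If the participant does not show up for their scheduled injection, the medication will be left in the refrigerator", where it is kept until that participant can be injected.

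Section 7.6 sets out the injection procedure for Cohort 1. Its first step is: "15 minutes prior to the scheduled appointment time, the study clinician will remove the injection from refrigeration". Nothing in that step refers to whether the participant has come. The section carries the step forward to later visits: "The same procedures (confirming appointments in advance, removal from refrigerator, injection administration" are among the items repeated for follow-up injections.

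Two other sections bear on a dose that has been out of the refrigerator. Section 9.0 lists, among other medication errors to be collected and reported, "storage at the wrong temperature, time outside refrigeration, use of expired medicine". Section 7.8 says that where a dose is judged to have been stored incorrectly, "the affected doses will be disposed of in a hazardous waste container".

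**The concern.** Sections 7.5 and 7.6 govern the same step, for the same doses, at the same site. One waits for a person and the other for a time on the clock. Staff working from 7.6 will take doses out before attendance is known; staff working from 7.5 will not.

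The difference matters most when the participant does not come, and the protocol expects that to happen: Section 4.1 names dropping out of care as the primary risk, and Section 7.7 is a stepwise plan for missed injections. Section 7.5 holds a no-show's dose for later use, and under 7.7 the participant may return days or weeks after the target date. If 7.6 was followed, that held dose has already been out once. No section says whether it may be returned, used later or discarded.

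Two things are at stake. One is consistent handling of the drug at the community site. The other is the medication-error record: Section 9.0 says errors will be sorted into four groups during analysis, and Section 1.2 asks whether consistent delivery is feasible in community settings. The number of handling events recorded there could depend on which section staff followed.

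**Working it through.** The plan states no figure on this point, so the check sets the two rules side by side.

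Let T be the scheduled time, A the participant's arrival and R the moment of removal.

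- Section 7.5: R is no earlier than A. If A never occurs, there is no removal.
- Section 7.6: R = T − 15 minutes, whatever A is.

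Both hold only if A is at or before T − 15 minutes. This gives three cases:

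1. *Arrives at least 15 minutes early.* Both rules can be met.
2. *Arrives after that point, on time or late.* Under 7.6 the dose is out before arrival, which 7.5 does not allow. With arrival L minutes after the scheduled time, the dose has been out for 15 + L minutes when the participant comes in; for an exactly punctual participant that is 15 minutes.
3. *Does not arrive.* Under 7.6 the dose is out from T − 15. The 7.5 instruction to leave it in the refrigerator can no longer be followed.

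Next, does case 3 amount to a recorded error or a discarded dose?

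- Section 9.0 names "storage at the wrong temperature, time outside refrigeration" but states no permitted time. Every dose that is given spends some time out to thaw under either section, so removal alone cannot be the error.
- Section 7.8 requires disposal only after a determination of incorrect storage, and gives no criterion for that determination.

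A no-show dose under 7.6 could therefore fall under either provision, but the text does not show that it must.

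How often case 3 would arise cannot be calculated, because the documents give no attendance rate. As an illustration only:

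- Section 11.2 puts 20 participants in Cohort 1.
- The Section 7.0 regimen table gives 4 injection visits on either bi-monthly schedule and up to 7 on the monthly schedule without lead-in.
- Scheduled visits: 20 × 4 = 80 to 20 × 7 = 140.
- Assumed unannounced no-shows of 10% to 20%: 80 × 0.10 = 8 to 140 × 0.20 = 28 doses removed under 7.6 that 7.5 would have kept in.
- If only 80% start, the level named in H1: 16 × 4 = 64 to 16 × 7 = 112 visits, so 64 × 0.10 = 6.4 to 112 × 0.20 = 22.4, or about 6 to 22 doses.

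Both ranges assume that everyone who starts stays on schedule. They count removals, not errors, wasted doses or harm. The conflict itself does not depend on them.

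**The case against.** The best defence has four parts.

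*Training.* Section 7.4 has pharmacy staff train all study staff in cold chain and thawing, and injecting clinicians read the instructions for use. Handling of a removed dose may be covered there. Those materials are not in the documents, though, and Section 7.4 does not say which trigger applies. Training can carry out a rule, but here it would first have to choose between two.

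*The specific rule governs.* Section 7.5 has an explicit no-show instruction and 7.6 has none, so 7.5 might be taken to prevail. That is a reasonable reading of intent. It does not help once a dose is already out, because leaving it in presupposes it was never removed, and it does not address on-time or late arrivals.

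*Reminders.* Section 7.1 provides contacts one week and one day before each injection, so some absences would be known before removal. This reduces how often the problem occurs; it does not remove the conflict.

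*Little depends on it statistically.* No hypothesis in Section 11.1 and no model in Section 11.3 uses error counts, and no between-cohort comparison of errors is planned. Section 9.0 also has near-miss and potential-error groups, so a dose never given need not raise a count of harm. All of this stands.

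A reader might go further and infer that each no-show under 7.6 creates a reportable medication error and a destroyed dose. The documents do not support that: 9.0 sets no time limit, 7.8 sets no criterion, and any stability limit for the product lies outside the documents. Nor are the two triggers flat opposites, since an early enough arrival satisfies both.

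**Conclusion.** The conflict is real and rests on the text alone. The two removal triggers are incompatible unless the participant arrives at least 15 minutes before the appointment, and the protocol does not say what becomes of a dose removed under 7.6 when nobody comes. Such a dose could count under Section 9.0 or Section 7.8, but the documents leave that open.

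The consequence is operational: how doses are handled at Project Trust, and whether the medication-error record means the same thing from visit to visit. No firm size can be given, since the illustrative counts rest on an assumed no-show rate and on full schedule adherence among those who start. It is a modest point, worth correcting because two stated operating rules disagree on a routine step. This review takes no position on which rule is right.

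**What to change.** The study clinicians and pharmacy should:

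- reconcile Sections 7.5 and 7.6 to a single removal trigger, worded identically in both places and applied to first and follow-up injections;
- state how a dose already removed is handled and recorded when the participant does not attend;
- align that statement with Section 7.8, by giving the criterion for incorrect storage, and with Section 9.0, by saying when time out of the refrigerator counts as an error and in which of the four groups it is placed.

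The choice of trigger and of any limit belongs to them. If a number of affected doses is quoted in support, it should be labelled as an illustration under assumed no-show rates. The cost is a short amendment and a training note, with no change to sample size or analysis.

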7.6 Injection Process and Safety Procedures

For patients enrolled in Cohort 1, injection procedures will be as follows:

- 15 minutes prior to the scheduled appointment time, the study clinician will remove the injection from refrigeration.
- Injections will be administered by a licensed healthcare professional (physician, nurse, nurse practitioner).
 - a. A complete dose will include two injections: one injection of cabotegravir and one injection of rilpivirine.
 - b. Each injection will be administered at separate gluteal injection sites during the same visit, with the ventrogluteal site recommended.
 - c. The clinician will consider the body mass index (BMI) of the patient to ensure that the needle length is sufficient to reach the gluteus muscle. Longer needle lengths (not included in the dosing kit) may be required for patients with higher BMI (greater than 30 kg/m²) to ensure that injections are administered intramuscularly as opposed to subcutaneously.
- The clinician and the participant will determine the target date for the next injection, which will occur between 25-32 days from initial injection. This discussion will happen while the participant waits for 15 minutes to ensure that no immediate adverse effects occur. This encounter and next planned injection date will be documented in the study Log Book by study staff. During this 15-minute period, the participant may also complete follow-up questionnaires if they are due for their three-month or six-month follow-up survey.
- Once the participant receives their second injection, they may discuss with their clinician whether they want to continue to receive their injection monthly, or whether they want to move to a bi-monthly schedule. The same procedures (confirming appointments in advance, removal from refrigerator, injection administration, monitoring period post-injection, scheduling of next injection, documentation in study log) will be used for follow-up injections
- Once the participant has been enrolled for at least 6 months in the study, they will be given the option to remain on CAB-RPV LA
 - a. That administration can take place either at PT or at CID depending on the participants preferences
 - b. If the participant wishes to receive their injection at CID, the study clinician will reach out to the participants CID provider so that the participant can begin to schedule their injections at CID

